In an effort to increase recruiting efforts, we will also approach potentially eligible patients identified in the EMR to have a gestation of 18 weeks or 19 weeks to provide information about the study and obtain the patient's interest in participating when they reach 20 weeks gestation. If the patient agrees to participate in the study, the study coordinator or designee will arrange for the patient to be consented during a scheduled prenatal visit, or arrange written, electronic consent when the patient reaches gestation of 20 to 34 weeks. The study coordinator or designee will either conduct the informed consent process in-person during a scheduled prenatal visit or provide written, electronic consent for all potentially eligible patients interested in participating. All potentially eligible participants will receive information on the purpose of the study, the procedures, expected risks and benefits, and a copy of the informed consent form to review. If a patient is approached during a prenatal care visit and is interested in participating, they will have the option of scheduling the informed consent process the same day or another day. The study coordinator (or member of the study team) will review the informed consent form with the participant and ensure comprehension through an oral review of key points.

The consent form will describe the purpose of the study, the procedures to be followed, and the risks and benefits of participation. An explanation will be provided about the use of PHI for research purposes and how confidentiality will be maintained as far as possible under the

Protocol Title: Minding the gap: improving women's health through coordinated postpartum planning

Federal Health Insurance Portability and Accounting Act (HIPAA). Written informed consent will be obtained from women who agree to participate in the study. A copy of the signed consent form will be given to the participant and documented in the participant's research record. No PHI will be retained for potential participants that do not qualify for the study or for those who elect not to participate in the study.

During the consent process, we will make it clear that participation is voluntary, and that there are no adverse consequences to choosing not to participate or to terminating participation at any time. The study coordinator will review the informed consent document with potential participants and explain in detail the purpose of the study, procedures, and risks.

In addition, we will prioritize recruitment of a bilingual, Spanish-speaking study coordinator and research assistants as Spanish is the most common non-English language among pregnant patients at Grady. If a patient agrees to participate, they will be randomized to an intervention/control study arm. All participants will receive an incentive of \$25 for enrolling in the study, \$25 after completing the 12- week survey, and \$25 after completing the 14-month survey. If randomized to the intervention arm, these participants will receive \$10 after each completed study visit. The number of study visits offered will depend on how far along a participant is in their pregnancy at enrollment. Participants will be offered up to (8) study visits and, if needed, 4 supplemental visits for a total of up to \$195 total compensation. If participants miss visits or do not finish the study, they will be compensated only for the visits and surveys they complete. Compensation will be provided via an e-gift card. Intervention arm participants will also be gifted a "Grady onesie" for their newborn during the delivery admission.

RCT Pilot: There will be no recruitment for the pilot.

14. Withdrawal of Participants

We do not anticipate any circumstances under which participants in Aim 1 or Aim 2 would be withdrawn without their consent. If participants choose to withdraw from the intervention study (Aim 2), the study coordinator will note this information, along with the reason, if known, in the study records. Medical record abstraction for this participant will be conducted for the period of time during which they were enrolled.

Participants in the RCT pilot will not be withdrawn.

15. Risks to Participants

There are potential (yet minimal) risks related to the conduct of this research study, including risks of breach of confidentiality and risk of some participants experiencing distress or revealing depression or intention for self-harm during the questionnaire and

Protocol Title: Minding the gap: improving women's health through coordinated postpartum planning

interview data collection, as the postpartum period is emotional and questions about social support or depressive symptoms may feel invasive.

16. Potential Benefits to Participants

Participants in this research study may not receive any benefit. However, participants in the intervention arm of the study may benefit from better continuity of care, more one on one time with a provider during prenatal care, and enhanced follow-up postpartum. In addition, the potential benefits of this research may extend to future postpartum patients at Grady Memorial Hospital or in other communities as these data are incorporated into the design of an EMR-integrated, culturally appropriate postpartum planning system.

17. Data Management and Confidentiality

Aim 1: All qualitative data will be professionally transcribed. These transcripts will be cleaned and de-identified prior to analysis. Once cleaned, we will use a team-based approach to systematically code each transcript using a qualitative software program called MaxQDA2020. Two researchers will review and code the transcripts with a lead analyst to identify emerging themes. We will use a directed approach to content analysis whereby the research theory will be used as guidance for data coding.

Aim 2: For Aim 2, we will conduct a randomized controlled trial to test the effectiveness of the comprehensive postpartum care system on postpartum care use and engagement. The primary outcome will be attendance at the postpartum visit occurring between 4-12 weeks after delivery. Secondary outcomes include receipt of early postpartum screenings for diabetes and hypertension (e.g., glucose testing or blood pressure checks), contraceptive initiation and use, use of medication for chronic conditions, pregnancy complications (including severe maternal morbidity), hospital readmissions, mental health status, perceived risks for SMM and cardiovascular disease, care plans and use, and satisfaction with care.

We will recruit 320 pregnant women between 20-34 weeks of gestation who receive 1 or more prenatal care visits in the Grady OB/GYN clinic, intend to deliver at Grady Memorial Hospital, have a documented diagnosis of chronic diabetes, chronic hypertension, pre-pregnancy obesity, gestational diabetes, and/or HDP and speak English or Spanish. We will assign participants to intervention or control arm using simple randomization. Participants will be randomized (1:1) to receive the postpartum care system (175) or standard of care (175) and will be followed for up to 14 months to allow ample time for attending the 4–12-week postpartum visit and to connect to primary and specialty care.

Power. Preliminary data suggest that 55% of women with HDP return for a postpartum follow-up visit in the absence of the intervention. Based on this, we should have 80% power to detect

Protocol Title: Minding the gap: improving women's health through coordinated postpartum planning

a risk ratio of 1.5 (or greater) with a sample of 292 women (146 in each arm), stratified evenly by chronic or new onset disease. To achieve this, 78% of women in the intervention arm would need to attend the postpartum visit, which is conservative. Assuming some (up to 15%) loss to follow-up, we should aim to recruit a sample of 320 women.

Analysis.

Primary outcome (Attendance at 4–12-week postpartum visit): We will compare the probability of attending the 4–12-week postpartum visit between intervention and control groups. We will fit log binomial models to estimate the effect (risk difference and relative risk) of the intervention on attendance at the 4–12-week visit, adjusting for diagnosis (chronic hypertension, chronic diabetes, pre-pregnancy obesity, gestational diabetes, or hypertensive disorder of pregnancy). If sample size permits, we will include relevant confounders, as appropriate.

Secondary outcomes: Secondary outcomes include receipt of recommended early postpartum screenings for diabetes and hypertension (e.g., glucose testing or blood pressure checks), contraceptive initiation and use, use of medication for chronic conditions, pregnancy complications (including SMM), hospital readmissions, mental health status, perceived risks for SMM and cardiovascular disease, plans for and use of primary and specialty care, and satisfaction with postpartum care. We will analyze these outcomes using log-binomial models to estimate relative risks and risk differences and 95% confidence intervals, adjusting diagnosis.

Implementation Analysis of existing RCT data: We will also conduct implementation analysis of intervention records and patient outcomes data to assess intervention fidelity and influences on equity in participation and primary and secondary outcomes. These data include study records in RedCap documenting number and timing of educational sessions, referrals and resources provided. We will also use data from two patient surveys implemented at 12 weeks and 14 months postpartum. We will compute descriptive statistics to determine the number of patients having received the full intervention. A preliminary definition for “receipt of full intervention” is if individuals received all 20 modules, had a complete postpartum care plan logged in Epic, received referrals for care, and appointment reminders. We will also analyze education module logs and will categorize patients as having received the content in the intended duration (over 8 study visits) or in a shortened time frame (e.g., in 2-3 visits). We will assess the extent to which the intended primary (receipt of a comprehensive postpartum visit) and secondary intervention outcomes (occurrence of SMM, primary care use, contraceptive use, and patient satisfactory with care) differ by level of implementation fidelity (dose and duration) using chi-square tests for association. We will also analyze quantitative study record data to describe the number of social service needs (e.g. housing, food, violence, etc.) and health needs (e.g. mental health) participants reported during the perinatal and postpartum

Protocol Title: Minding the gap: improving women's health through coordinated postpartum planning

period. We will assess the relationship between patients' social needs and barriers to meeting those needs with primary and secondary outcomes. We will assess the extent to which the intended primary (receipt of a comprehensive postpartum visit) and secondary intervention outcomes (occurrence of SMM, primary care use, contraceptive use, and patient satisfactory with care) differ by level of social needs and experiences of barriers to completing referrals using chi-square tests for association. We will compute descriptive statistics and tests of significance using SAS 9.4.

Protection against risks. As a research team, we will protect against risks and potential risks in a number of ways. A primary mechanism for protecting against risks will be ensuring intensive training of the research team. First, the MPI's will require all of the research team members to complete Human Subjects Research Training, as documented through their successful completion of the Human Subjects Collaborative Institutional Training Initiative (CITI) modules, available at: <https://www.citiprogram.org/>. Second, the investigative team will conduct several in-depth trainings of all research staff prior to the recruitment of any research participants that will include an overview of the entire research plan and protocol and specific trainings to address recruitment, enrollment, and informed consent procedures; questionnaire data collection; and clinical data collection through the electronic medical record; and secure maintenance of confidentiality and security of all data streams and participant confidentiality.

In particular, the research team members having face-to-face interaction and/or telephone interaction with the research participants will be trained in the following potential risks and strategies for protecting against these risks prior to initiation of any participant recruitment.

Confidentiality: Confidentiality will be maintained on several levels. First, all research investigators and staff are fully trained, and required to maintain training, in human research protections, including the most up-to-date strategies for maintaining the confidentiality of research data. Second, all data will be protected from anyone who does not have a staff position in the study. Third, the raw data will be kept in password protected OneDrive files or on a HIPAA compliant database (e.g., REDCap), accessible only to a limited number of the research team. No one will have access to the data or the identifying information other than the study investigators and designated study staff, directly involved. Fourth, all data entry will be done on password-protected and encrypted tablet computers with REDCap, which is a software that allows for the transfer of data to the Emory server over the internet in a HIPAA-compliant, encrypted manner. Deidentified transcripts will be stored on REDCap and OneDrive, both of which are compliant with Emory University's HIPAA security policies and procedures; Fifth, the Emory server is password-protected, encrypted, and backed up to ensure data confidentiality and integrity; Sixth, data for analyses will be stripped of all PHI

Protocol Title: Minding the gap: improving women's health through coordinated postpartum planning

identifiers; Seventh, the data will be kept until they are fully analyzed and destroyed when they are no longer needed. Upon completion of the conduct of the protocol, the subject log linking study identifiers to subject identity and PHI will be destroyed.

RCT Pilot: We will use the same data management protocols as in Aim 2. However, data will be destroyed once instruments are finalized. No data will be analyzed.

18. Provisions to Monitor the Data to Ensure the Safety of Participants

Aim 2 is a clinical trial and will have a Data and Safety Monitoring Plan. An individual's participation in the clinical trial aspect of this study meets Federal Regulations defining minimal risk: "minimal risk means that the probability and magnitude of harm or discomfort anticipated in the research are not greater in and of themselves than those ordinarily encountered in daily life or during the performance of routine physical or psychological examinations or tests." [§46.102]. The intervention itself (enhanced postpartum care system) does not pose a risk for adverse events, however, as eligibility criteria for participation in the clinical trial include having chronic hypertension or diabetes or experiencing cardiometabolic complications during pregnancy, it is possible that a non-study related adverse event may occur to enrolled participants. We believe that the enhanced postpartum care system may help in the early identification and prevention of complications, as participants in the intervention arm will receive additional follow-up postpartum. As part of the study, the study coordinator will monitor any readmissions or complications using the EMR and, as reported on the surveys conducted at 12-weeks and 14-months postpartum.

We have constituted a Data Safety Monitoring Board (DSMB) to review safety and study enrollment of participants in this study, which will meet on an annual basis. The DSMB will review in tabular form any and all Adverse Events (AEs); in narrative, any and all Serious Adverse Events (SAEs); enrollment data; attrition data; data quality and completeness; and narrative reports of any issues around loss of participant confidentiality. Serious adverse events will be reported to the IRB within 7 days of the study team becoming aware of the occurrence of the event; any deaths will be reported within 24 hours of the team becoming aware of the event. The report of DSMB's annual review to the Emory University IRB annually.

The DSMB responsibilities are to:

1. Review the research protocol, informed consent documents, and plans for data safety and monitoring prior to beginning enrollment;

Protocol Title: Minding the gap: improving women's health through coordinated postpartum planning

2. Evaluate the progress of interventions, including periodic assessments of data quality, participant recruitment, accrual and retention, participant risk versus benefit, performance of the site, and other factors that can affect study outcome;
3. Consider factors external to the study when relevant, such as scientific or therapeutic developments that may have an impact on the safety of the participants or the ethics of the trial;
4. Ensure the rights and safety of the study participants are protected;
5. Report on the safety and scientific progress of the trial;
6. Make recommendations to the PI, and research ethics board/institutional review board about any determination, or other modifications of the trial based on the observed beneficial or adverse effects of the treatment under study.

DSMB Membership

1. Members of the DSMB have been invited by [name]; members will be completely independent of the trial investigators and have no financial or scientific conflict of interest with the study. A potential conflict that develops during a member's tenure on the DSMB must be disclosed and, if significant, will lead to replacement of the DSMB member.
2. Disciplines represented on the DSMB will include health professionals with expertise in obstetrics and gynecology, family medicine, internal medicine, and epidemiology or biostatistics.
3. A Chairperson will be selected prior to the first meeting. The Chair will lead all meetings, coordinate meetings and communications, develop the agenda, and produce meeting minutes and reports.

DSMB Meetings. The first meeting will take place before initiation of the trial to discuss the protocol and to establish guidelines to monitor the study. The Chair, with input from [name], will prepare the initial agenda, which should address issues concerning commencement of the trial. The initial tasks of the DSMB are to review the protocol and informed consent forms with regard to subject safety, review this charter and amend it, if necessary, and discuss the plan for monitoring data, subject safety, and compliance. [name] will distribute the proposed reports to DSMB members prior to each subsequent meeting. Following the initial meeting, the DSMB will convene at least once per year to review accumulated data on safety. Meetings shall be convened face-to-face or by teleconference, at the DSMB members' discretion. If a question of patient safety arises or if a Serious Adverse Event occurs, an emergency meeting of the Board may be

Protocol Title: Minding the gap: improving women's health through coordinated postpartum planning

called at any time by the Chairperson. The format for DSMB meetings will consist of two sessions. The first session will be attended by the PIs where the conduct and progress of the study, subject accrual, and subjects' compliance with protocol, general safety issues, and any other problems encountered will be discussed. The second session will be open only to DSMB members. Safety and efficacy data, the general conduct of the trial, outcome results, and adverse events are presented at this session.

19. Provisions to Protect the Privacy Interests of Participants

Aim 1: In-depth interviews will be conducted via phone, Zoom, FaceTime or Google Duo (according to patient preference). Patients will have the ability to decide when and where to take part in the interview. The privacy interests of all participants will be protected during the interviews. We will describe the study procedures at the time of the screening call as well as at the beginning of the interview. This information will detail our procedures for collecting, storing, and de-identifying the qualitative interview data. In addition, we will explain the interview process and identify each staff member (interviewer, note taker) who will be present during the interview. If a participant expresses concerns about his/her privacy or confidentiality, we will respond accordingly. This may include asking the note taker not to participate in the interview or not to record the interview.

Aim 2: The study coordinator will approach potential participants either before or after their prenatal care visit and will invite them to a private clinic room for recruitment. For women in the intervention arm, postpartum planning visits will also take place in a private room before or after prenatal care. After women deliver, the coordinator will schedule a time to meet with participants in their private room and finalize their postpartum care plan.

RCT Pilot: There will be no recruitment or participation during the pilot phase.

20. Economic Burden to Participants

There are no costs to the study participants.

21. Consent Process

Aim 1:

- a) We are requesting a partial HIPPA waiver for the purpose of identifying and recruiting prospective research participants for enrollment. We will use the Grady Obstetric and Gynecologic Outcomes database (IRB00103211) to identify women meeting the study criteria who delivered at Grady during the past year.

Review of PHI is necessary to determine whether potential participants are eligible for this study, and it is impracticable to ask all women delivering at GMH to sign an authorization to access their PHI to determine eligibility. Only the PI and study coordinator will have access to PHI. No PHI will be retained for potential participants that do not qualify for the study. If the potential participant does qualify for the study, PHI will be retained for recruitment purposes.

- b) We will obtain written consent prior to the start of the remote follow-up session using REDCap. This consent process will take approximately 5 minutes and will allow for the participants to ask questions about the consent process or study purpose.

Aim 2:

- a) We are requesting a partial HIPPA waiver for the purpose of identifying and recruiting prospective research participants for enrollment. We will use the daily appointment schedules and medical record data to identify women with prenatal care visits who meet the study criteria. Review of PHI is necessary to determine whether potential participants are eligible for this study, and it is impracticable to ask all women attending a prenatal care visit to sign an authorization to access their PHI to determine eligibility. Only the PI and study coordinator will have access to PHI. No PHI will be retained for potential participants that do not qualify for the study. If the potential participant does qualify for the study, PHI will be retained for recruitment purposes.
- b) We will obtain informed consent from all women who agree to participate in the study. The consent process will take place in a private clinic room or office when conducting consent in-person, and in a private space when conducting and obtaining written, electronic consent via REDCap, during phone recruiting and will take approximately 15 minutes. During the consent process, we will make it clear that participation is voluntary, and that there are no adverse consequences to choosing not to participate or to terminating participation at any time. The study coordinator will review the informed consent document with potential participants and explain in detail the purpose of the study, procedures, and risks. A copy of the signed consent form will be given to the participant and documented in the participant's research record. No PHI will be retained for potential participants that do not qualify for the study or for those who elect not to participate in the study.

Protocol Title: Minding the gap: improving women's health through coordinated postpartum planning

- c) For women who report receiving care outside of Grady in the year postpartum, we will ask women to sign an 'Authorization of Release of Information' allowing the study team to access their medical records at the other provider.

RCT Pilot: We are requesting a *full HIPPA waiver* for this pilot phase, for the purposes of review and abstraction only, of the EMR for patients that meet the criteria for enrollment. These patients will not actually be recruited or consented/enrolled; the purpose of review and abstraction is solely to design and test the REDCap instruments and EMR (Epic) care plan to prepare for implementation and start of the randomized trial (Aim 2).

Non-English-Speaking Participants

Approximately 23% of Grady obstetric patients are non-native English speakers. Spanish is the predominant language of non-English speaking women (76%), followed by Amharic (12%) and French (6%).

Aim 1: Due to budget concerns associated with transcription and translation costs for interviews conducted in languages other than English, will only recruit English-speaking participants for the in-depth interviews. All consents and interviews will be in English.

Aim 2: We will recruit English and Spanish speaking participants. It is not practicable to translate all study material and surveys into multiple languages, and English and Spanish are the most common languages among pregnant Grady patients. We will translate all consent forms, educational materials, and surveys into Spanish and will hire a bilingual study coordinator.

Participants who are not yet adults (infants, children, teenagers)

For Aim 2, we will use EMR data to determine the age of prospective participants. If patients are eligible (have a diagnosis of chronic hypertension or diabetes, gestational diabetes, and/or HDP), we will include pregnant women <18 years of age in Aim 2. As women ages 14-18 years of age are able to receive prenatal care without parental consent in Georgia, we will request a waiver of parental consent for enrolling pregnant minors into the study. For pregnant minors, a member of the study team with experience working with minors will conduct the informed consent process. Minors will receive the same information as women ≥ 18 years of age but will undergo a longer conversation to ensure comprehension. Minors will sign the informed consent form if they agree to participate, and the study team member determines they understand the information on the study.

Cognitively Impaired Adults

Protocol Title: Minding the gap: improving women's health through coordinated postpartum planning

We will not include cognitively impaired adults as they may require additional support for postpartum care planning and therefore would not be appropriate candidates for this intervention.

Adults Unable to Consent

We will not include adults unable to consent.

22. Setting

Aim 1: Recruitment and in-depth interviews will take place over the phone or virtually.

Aim 2: Recruitment will take place at the OB/GYN at Grady Memorial Hospital. For participants in the intervention arm, postpartum care planning visits will take place in the Grady clinic and in the postpartum ward (after delivery). All participants will fill out surveys remotely. The study coordinator will be assigned a dedicated space in the Emory Faculty Building, adjacent to Grady.

RCT Pilot: This pilot phase will take place in the OB/GYN clinic at Grady Memorial Hospital.

23. Resources Available

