Once the study results are publicly disseminated, we will inform the study participants via text, email, or telephone, depending on their preferred means of contact. Aim 2 participants with an active account will be able to view the postpartum plan via MyChart. For participants without an active MyChart account, the postpartum plan will be printed for them. We will work with the Community Advisory Board for this study to disseminate results broadly to the communities served by Grady.

9. Study Timelines

Aim 1: Each in-depth interview is expected to last approximately 30 minutes. Each participant will be interviewed only once. We anticipate that it will take approximately one month to enroll all interview participants. We estimate that the qualitative data will be analyzed by the end of Year 1.

Aim 2: Individuals will participate in the study for approximately 18 months (starting during prenatal care and continuing 14 months after delivery). There are approximately 200 deliveries per month at Grady. Assuming that 40% of women will be eligible (data

Protocol Title: Minding the gap: improving women's health through coordinated postpartum planning

from our study suggests that 38% of women at Grady have hypertensive disorders²⁶⁾ and about 15% of women will not receive any prenatal care, and 50% will agree to participate in the study, we expect recruitment to take about 9 months. We estimate that data from the randomized trial will be analyzed during Year 5.

RCT Pilot: The piloting will be iterative and will occur between May and July 2022.

Study Timeline

	Year 1				Year 2				Year 3				Year 4				Year 5			
	1	2	3	4	1	2	3	4	1	2	3	4	1	2	3	4	1	2	3	4
Project launch	1																			
1 Develop questions for interviews		1																		
1 Conduct interviews			1																	
1 Analyze qualitative data				1																
2 Develop content for care system					1															
2 Design and test EMR tool						1														
2 Study start up							1													
2 Enroll women								1												
2 Follow women for 14 months									1											
2 Conduct follow-up surveys										1										
Analyze/disseminate RCT results											1									
Prepare manuscripts												1								

10. Inclusion and Exclusion Criteria

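### The stated 80% power rests on an HDP-only control rate and reproduces only within an even chronic/new-onset split that no rule delivers; it describes neither the enrolled mix nor the overall comparison

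*Combined protocol and SAP*

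**What the plan says.** Section 17 (Power) gives one usual-care rate: "Preliminary data suggest that 55% of women with HDP return for a postpartum follow-up visit in the absence of the intervention". It continues: "Based on this, we should have 80% power to detect" "a risk ratio of 1.5 (or greater) with a sample of 292 women (146 in each arm), stratified evenly by chronic or new onset disease". It then says that "78% of women in the intervention arm would need to attend the postpartum visit, which is conservative". No significance level is given, and the paragraph does not say whether the 80% is for the whole comparison or for each disease group.

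The Aim 2 text in the same section requires that women "have a documented diagnosis of chronic diabetes, chronic hypertension, pre-pregnancy obesity, gestational diabetes, and/or HDP and speak English or Spanish". Section 2 defines HDP as gestational hypertension or preeclampsia and lists it apart from the other four conditions. The amendment log shows that pre-pregnancy obesity became eligible with version 9. The current power paragraph mentions neither obesity nor diabetes.

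Section 10 sets no quota by diagnosis. Section 5 allocates by minimization on diagnosis and Section 17 by simple randomization.

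**The concern.** A power statement is only as good as its control rate, and this one comes from one of the five eligible groups. Usual care differs by diagnosis: under Section 6 only women with HDP are automatically scheduled for a home blood-pressure visit. The endpoint may differ too. The 55% counts a follow-up visit that is not further defined, whereas Section 6 has two blinded physicians decide whether a visit was a comprehensive postpartum visit.

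The clause "292 women (146 in each arm), stratified evenly by chronic or new onset disease" adds a second difficulty. It implies that half the sample has chronic disease, yet supplies no rate for that half, and nothing in the design makes the halves equal.

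At stake is how the result is read. If the trial finds no difference, readers will ask what effect it could have detected. The paragraph answers with a power figure that does not match the comparison the primary analysis makes.

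**Working it through.** **Inputs.** Control 0.55, intervention 0.78 and 146 per arm come from Section 17 (Power). An even split gives 146 / 2 = 73 per arm in each disease group. Two-sided alpha of 0.05 is an assumption.

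**Formula.** Power = Φ{ [ (p2 − p1) − c − 1.96·√(2p̄(1−p̄)/n) ] / √([p1(1−p1) + p2(1−p2)]/n) }, where p̄ is the mean of p1 and p2. The continuity correction c is 1/n where used and 0 otherwise.

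**1. Reproducing the 80%.** With n = 73, p̄ = 0.665 and c = 1/73 = 0.0137:
(0.23 − 0.0137 − 1.96 × 0.0781) / 0.0758 = 0.834, so power is 79.8%.
Fisher's exact test gives 80.3% and a Wald test on the log risk ratio 81.2%. Without continuity correction the figure is 84.5%. The continuity-corrected sample size is 74 per arm per group, 296 in total, close to the plan's 292. The 80% is therefore recovered as power within one half of an even split. That reading is inferred from the arithmetic; the plan does not state it.

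The stated risk ratio does not recover it: 0.55 × 1.5 = 0.825, which gives 93.5% at 73 per arm (continuity-corrected) and 99.9% at 146. The planned 78% is a risk ratio of 0.78 / 0.55 = 1.418.

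**2. Overall comparison, same rates.** With n = 146 and c = 0:
(0.23 − 1.96 × 0.0552) / 0.0536 = 2.272, so power is 98.8% (98.4% with continuity correction).

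**3. If the split is not even.** Take 30/70 as an illustration. The smaller group has 0.30 × 146 = 43.8 per arm. Continuity-corrected power for 55% against 78% is 52.9% at 43 per arm and 54.1% at 44.

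**4. Overall power if the control rate is not 55%.** The document gives no rate for the eligible mix, so 40-70% is an assumed range (146 per arm, no continuity correction).

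| Control | RR held at 1.418 | +23 points held | Intervention held at 78% |
|---|---|---|---|
| 40% | 81.9% | 97.9% | >99.9% |
| 45% | 90.2% | 98.0% | >99.9% |
| 50% | 95.9% | 98.4% | 99.9% |
| 55% | 98.8% | 98.8% | 98.8% |
| 60% | 99.8% | 99.3% | 91.8% |
| 65% | >99.9% | 99.7% | 69.4% |
| 70% | >99.9% | 99.9% | 34.3% |

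Power crosses 80% at a control rate of about 39% when RR is held, and at about 63% when 78% is held. With +23 points held it does not cross 80% in this range.

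**5. Effect detectable with 80% power, 146 per arm.**

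| Control | Intervention rate | RR |
|---|---|---|
| 40% | 56.3% | 1.41 |
| 50% | 66.1% | 1.32 |
| 55% | 70.8% | 1.29 |
| 60% | 75.3% | 1.25 |
| 65% | 79.6% | 1.22 |
| 70% | 83.8% | 1.20 |

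**The case against.** The strongest reply is that the overall comparison has a large reserve, so an imperfect control rate does little harm. That stands. A reader might infer that the trial is underpowered, or that 80% is wrong for the enrolled women. The document supports neither, because it gives no attendance rate for the mix. Its hints also point both ways. Section 3 says that up to 40% of US women miss postpartum visits, which implies attendance of at least 60%. It also says that use is lowest where complications and chronic conditions are most common. The steep losses in the last column of step 4 require the intervention rate to stay at 78% while controls rise, and Section 17 presents 78% as the rate needed, not as a forecast.

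Two other tempting inferences fail:
- The even split might seem to cap HDP at half the sample. But diagnoses are combined with and/or, so a woman with chronic disease may also have HDP. Section 9 also puts hypertensive disorders at 38% of Grady women beside an assumed 40% eligible, so an HDP rate is not a remote proxy.
- Section 9 assumes that "about 15% of women will not receive any prenatal care, and 50% will agree to participate in the study", which might suggest that enrolled controls attend more often than the women behind the 55%. How those women were selected is not stated, so the contrast is undocumented.

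It can also be said that deleting the even-split clause removes the one phrase that makes 80% reproducible. That is so, which is why the figure must be restated along with the deletion. Finally, version 13 refers to data already collected, so a restatement changes neither conduct nor analysis. Its value lies in interpretation.

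**Conclusion.** The point holds in a limited form. The 80% is unsupported for the enrolled population, because its only control rate belongs to one of five eligible diagnoses and nothing justifies carrying it over. It is also not the power of the overall primary comparison, which is about 99% on the plan's own rates. It matches only within-group power at 73 per arm under an even split. Minimization and randomization balance the arms; they do not fix how many women of each type enrol. At a 30/70 split the smaller group would have about 53%.

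Whether overall power is really below 80% cannot be determined from the document. On the assumptions used (two-sided 5%, 146 per arm analysed), that would need controls above about 63% with the intervention rate held at 78%, or below about 39% at a risk ratio of 1.42. The conclusion does not depend on retention: if the plan's full 15% loss occurred among 320, 320 × 0.85 = 272 women (136 per arm) would remain, and 55% against 78% would still have 98.3% power.

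**What to change.** Rewrite the power paragraph in Section 17:
- Remove the clause about even stratification by chronic or new-onset disease, and state that the power is for the overall comparison, with the significance level.
- Replace the 80% with power and detectable effect at 146 per arm over a control range such as 40-70%. Show both the fixed-RR and the fixed-78% scenarios, as in steps 4 and 5.
- Say that 55% is an HDP-only rate. If existing Grady records allow, replace it with historical usual-care attendance at 4-12 weeks among women who meet the current Section 10 criteria, without using trial outcomes. Note that such a rate only approximates the physician-adjudicated endpoint and cannot reflect consent. The document does not show that the Grady outcomes database alone can supply it: Section 21 uses it to identify Aim 1 women, and Section 6 for emergency and urgent-care visits.

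Leave the enrolment target unchanged. The cost is a rewritten paragraph, a records query if one is feasible, and possibly a less favourable figure.
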